4.4 Rationale for Radium-223 for Bone Metastases in Prostate Cancer

Radium-223 is an alpha-emitting radioisotope which is a bone-seeking calcium mimetic. It selectively targets the area with increased bone turnover, especially within the microenvironment of osteoblastic or sclerotic metastases. It has been approved by FDA for the treatment of metastatic castrate-resistant prostate cancer (mCRPC) with symptomatic bone metastases and without known visceral disease based on its ability to extend overall survival as shown its pivotal phase III trial. Unlike beta particle emitting radiopharmaceuticals, radium-223 emits high-energy alpha particles of short range (<100 μ m) thus saving the surrounding healthy tissues and significantly reducing unwanted myelotoxicity.

Radium-223 was approved by the US FDA on May 15, 2013 based on the interim results from a Phase III randomized trial, the ALSYMPCA study (Alpharadin in the treatment of patients with symptomatic bone metastases in castration-resistant prostate cancer). In this trial, 921 patients who had received, were not eligible to receive, or declined docetaxel were randomly assigned in a 2:1 ratio to receive six injections of radium-223 (at a dose of 50 kBq per kilogram of body weight intravenously (55 kBq/kg after implementation of NIST standard update) every 4 weeks or matching placebo. At the interim analysis, which involved 809 patients, radium-223, as compared with placebo, significantly improved overall survival (median, 14.0 months vs. 11.2 months; HR=0.70; 95% CI, 0.55 to 0.88; two-sided P=0.002). The updated analysis involving 921 patients confirmed the radium-223 survival benefit (median, 14.9 months vs. 11.3 months; HR=0.70; 95% CI, 0.58 to 0.83; P<0.001). The rate of AEs was consistently lower in the radium-223 group than in the placebo group for all AEs (93% vs. 96%), grade 3 or 4 AEs (56% vs. 62%), and serious AEs (47% vs. 60%). There were no clinically meaningful differences in the frequency

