5.1 Inclusion Criteria

- 5.1.1 Patient must have at least one and up to three asymptomatic metastatic tumor(s) of the bone or soft tissue (with at least one bone metastasis) within the past 3-months that are ≤ 5.0 cm or <250 cm 3 as seen on either CT/MRI scan and/or bone scan. Up to five lesions are allowed on advanced functional imaging such as fluciclovine (Axumin), choline or ^{18}F -DCFPyL (“PyL”) PET-CT scan within the past 6-months. (PET-CT scan is reasonable for study entry imaging as an alternative to CT/MRI scan and/or bone scan)
- 5.1.2 Patient must have had their primary tumor treated with surgery and/or radiation.
- 5.1.3 Histologic confirmation of malignancy (primary or metastatic tumor).
- 5.1.4 PSADT <15 months. PSA doubling time (PSADT) will be calculated using as many PSA values that are available from time of relapse (PSA > 0.2). To calculate PSADT, the Memorial Sloan Kettering Cancer Center Prostate Cancer Prediction Tool will be used. It can be found at the following web site: <https://www.mskcc.org/homograms/prostate/psa-doubling-time>.
- 5.1.5 Patient may have had prior systemic therapy and/or ADT associated with treatment of their primary prostate cancer. Patient may have had ADT

associated with salvage radiation therapy (to the primary prostate cancer or pelvis is allowed).

5.1.6 PSA ≥ 0.5 but ≤ 50 .

5.1.7 Any testosterone lab within the past 6 months $> 50\text{ng/dL}$.

5.1.8 Patient must be ≥ 18 years of age.

5.1.9 Patient must have a life expectancy ≥ 12 months.

5.1.10 Patient must have an ECOG performance status ≤ 2 .

5.1.11 Patient must have normal organ and marrow function as defined as:

Before the first administration of Xofigo, the absolute neutrophil count (ANC) should be $\geq 1.5 \times 10^9/\text{L}$, the platelet count $\geq 100 \times 10^9/\text{L}$ and hemoglobin $\geq 10 \text{ g/dL}$.

5.1.12 Patient must have the ability to understand and the willingness to sign a written informed consent document.

5.1.13 LDH lab performed within 6 months of enrollment.

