APPENDIX IX: RAPID SPECT Imaging Sub-Contract Study

Purpose: To measure radiation exposure to specific metastases by performing SPECT scans at 2-4 hours, 24 hours (+/- 4 hours), and 48 hours (+/- 4 hours) following Xofigo infusions #1 and #6 to calculate the total radiation exposure to the specific metastases.

All patients participating in Hopkins Xofigo/XRT (RAVENS) trial will be eligible for participation in the Rapid SBIR-contract supported CX α RPT (companion) trial.

Patient treatment will not change. A data collection effort for retrospective evaluation of results will be conducted by Hopkins via a companion protocol that patients participating in the parent trial may sign on to. The target population is 20 out of the 30-34 patients that will be enrolled in the SABR + Xofigo arm of the RAVENS trial. The expected accrual is 10 patients in year 1 and 10 patients in year 2.

Patients will be compensated with a \$100 gift card for the 3 ^{223}Ra SPECT/CT scans following Xofigo infusion #1, and a \$100 gift card for the 3 ^{223}Ra SPECT/CT scans following Xofigo infusion #6. gift cards and scans will be paid for by the research budget from the NIH sub-contract.

Hypothesis: The ^{223}Ra dosimetry calculations performed will demonstrate, retrospectively, that > 30% of the patients would have required an adjustment in the XRT treatment plan, to meet the following criteria:

[figure not shown]
1. Tumor absorbed dose (to at least 5 lesions) \geq 80 EQD2 -Gy (BED=96 Gy; $\alpha/\beta=10$ Gy),
2. Normal organ doses within tolerance limits.

[figure not shown]
Data/Workflow:

- For patients participating in the RAVENS protocol, Hopkins will collect ^{223}Ra SPECT/CT at 2-4 hours, 24 hours (+/- 4 hours), 48 hours (+/- 4 hours) after first and last Xofigo infusion.
- Rapid receives anonymized SPECT projection data, performs quantitative recon, 3D-RD dosimetry, and provides combined RPT-XRT (CXRPT) dose map to Hopkins.
- Hopkins compares XRT dose map w/ and w/o α RPT dosimetry and determines if a change would have been merited.
- Rapid receives Hopkins assessments.

Standard Operating Procedure
Quantitative Imaging and Dosimetry of Radium-223
V2.2; July 8, 2019

Characteristics of Ra-223	Radium-223 is primarily an alpha emitter (95.3% abundance). The fractions emitted as beta and gamma particles are 3.6% and 1.1%. The gamma component allows for the in-vivo imaging.																																																		

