Image quantification procedure	SPECT projections will be reconstructed using previously published iterative quantitative reconstruction methods established by Rapid ²⁻⁵ . Volume of interest (VOIs) will be drawn around the major organs and lesions of interest at each time points. Total counts in the VOIs at each time point will be calculated and converted to activity by measured sensitivity. The time integrated activity coefficients (TIACs), mathematically equivalent to the number of decays per unit injected activity, will be calculated from single or double exponential fits for the main source organs and the lesions. The TIACs in the red marrow (TIACRM) will be derived from contours drawn around lumbar vertebrae L3-L5, the TIACRM will be divided by the marrow mass in this region to give TIACRM concentration. Total TIACRM will be obtained as the product of this concentration and the estimated patient RM mass.
Dosimetry analysis procedure	The absorbed dose values for target organs will be derived by using whole organ S-value based method and MC-calculation using images and 3D-RD approach (RBE =5 for alphas). Importantly, Rapid follows SNMMI MIRD Committee recommendations as published in its series of pamphlets and will update calculation accordingly if necessary. Mean absorbed dose (mAD) and mean (mBED) will be obtained using the software package 3D-RD ⁶⁻¹⁰ . The methodology used in 3D-RD is briefly summarized below: 
 1. Using the Electron Gamma Shower (EGS) Monte Carlo (MC) software, one million events will be run for the beta- and photon components of the isotope decay spectra, for each time point. 2. The energy deposition distribution from the contributing components from MC will be weighted for probability and unit activity then converted to absorbed dose rate for each VOI (spectra probability distributions obtained from LBL/Lund web site¹¹). 3. The dose rates for the each VOI will be fitted using the simulation Analysis and Modeling II (SAAM II) software package (The Epsilon Group, Charlottesville VA), and the area under the curve calculated as the absorbed dose mAD. 4. The mBED will be calculated using the linear-quadratic (LQ) BED methodology described in reference¹².

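### Appendix IX takes red-marrow activity from L3-L5 in every man and scales it to the whole marrow without excluding a vertebra that holds a metastasis, so the marrow value is misstated in men with disease there.

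*Combined protocol and SAP*

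**What the plan says.** The rule is in Appendix IX, in the row on image quantification. It has three steps.

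- Region: "The TIACs in the red marrow (TIACRM) will be derived from contours drawn around lumbar vertebrae L3-L5".
- Concentration: "the TIACRM will be divided by the marrow mass in this region to give TIACRM concentration".
- Scaling: "Total TIACRM will be obtained as the product of this concentration and the estimated patient RM mass".

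The same row provides for lesion regions: "Volume of interest (VOIs) will be drawn around the major organs and lesions of interest at each time points". It does not say what happens when a lesion region lies inside the L3-L5 contour. The next row, on dosimetry analysis, adds a general statement: "Rapid follows SNMMI MIRD Committee recommendations as published in its series of pamphlets and will update calculation accordingly if necessary".

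Three other places bear on the point. Section 5.1 admits only men "with at least one bone metastasis". Section 5.2 excludes actual or impending cord compression but not vertebral metastasis. Section 4.4 describes radium-223 as taken up where bone turnover is raised, "especially within the microenvironment of osteoblastic or sclerotic metastases".

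The companion study aims for 20 men from the combination arm, scanned after infusions #1 and #6. Appendix IX calls the imaging exploratory, says treatment will not change, and plans to publish on variability between patients and the influence of tumour burden.

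**The concern.** L3-L5 serves as a sample of normal marrow. The method works only if that sample represents the rest of the marrow. A metastasis in one of the three vertebrae breaks this condition, and the drug is one that seeks out such lesions. Taken as written, the rule counts the lesion's activity as marrow activity, divides it by a marrow mass, and carries the inflated concentration to the whole skeleton. One local lesion is read as if it were everywhere. The same counts can also appear in the lesion result.

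Red marrow matters in this substudy. In Appendix IX's own table it has the second-highest dose per unit activity (0.13879 Gy/MBq), after osteogenic cells (1.15206 Gy/MBq). The error arises only in men with tumour in L3-L5. It therefore adds spurious spread between patients and can make marrow dose appear to rise with tumour burden. Those are the two relations the substudy intends to report.

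**Working it through.** The documents give no figure for this error, so there is none to reproduce. The check follows the rule algebraically.

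**Inputs.** The three-step rule comes from Appendix IX. Three quantities are not in the documents and are assumed:

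- f, the fraction of the L3-L5 region filled by lesion: 5% to 33% (one third is one whole vertebra of three of equal size).
- r, lesion uptake relative to normal: 2 to 10. Section 4.4 supports r > 1 but gives no number.
- s, the share of all marrow that lies in L3-L5: 5% to 10%.

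**Step 1: the rule.** Total = (activity in L3-L5 ÷ marrow mass in L3-L5) × patient marrow mass.

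**Step 2: a lesion in the region.** With normal concentration c, the measured concentration is (1 − f)c + f·r·c = c[1 + f(r − 1)]. The scaling is linear, so the whole-marrow value carries the same factor, 1 + f(r − 1).

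| r | f = 5% | f = 10% | f = 20% | f = 33% |
|---|---|---|---|---|
| 2 | 1.05 | 1.10 | 1.20 | 1.33 |
| 3 | 1.10 | 1.20 | 1.40 | 1.67 |
| 5 | 1.20 | 1.40 | 1.80 | 2.33 |
| 10 | 1.45 | 1.90 | 2.80 | 4.00 |

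At r = 1 there is no error. Below 1 it reverses: r = 0.5 gives 0.975 at f = 5% and 0.83 at f = 33%.

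**Step 3: counting the lesion in the true total.** The true total then rises by s·f(r − 1), and the factor is [1 + f(r − 1)] ÷ [1 + s·f(r − 1)]. The lowest value is 1.05 ÷ 1.005 = 1.04 (r = 2, f = 5%, s = 10%). The highest is 4.00 ÷ 1.15 = 3.48, about 3.5 (r = 10, f = 33%, s = 5%).

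**Step 4: direction by infusion.** Section 6.8 places SABR within 60 days of randomization. Six injections four weeks apart put infusion #6 at 5 × 28 = 140 days after infusion #1. By then the lesion is scheduled to have been irradiated, so r > 1 is less secure for the second of the two scan sets.

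**Step 5: effect on a 20-man mean.** Suppose true doses are equal and 2 to 4 men are affected (an assumed number).

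- Factor 1.2: (18 + 2 × 1.2) ÷ 20 = 1.02 and (16 + 4 × 1.2) ÷ 20 = 1.04, a rise of 2% to 4%.
- Factor 2.33: (18 + 2 × 2.33) ÷ 20 = 1.13 and (16 + 4 × 2.33) ÷ 20 = 1.27, a rise of 13% to 27%.

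**Step 6: after correction.** Leaving out involved vertebrae, or removing the lesion from both activity and mass, sets f to 0. The factor for uninvolved marrow is then 1.00.

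**The case against.** The strongest reply is that the text nowhere says involved vertebrae are to be used. Lesions have their own regions, the imaging vendor follows published dosimetry recommendations, and the companion protocol that men sign is not part of these documents and may settle the matter. A competent analyst would probably avoid an obvious lesion.

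Part of this stands: use of an involved vertebra is inferred from an unconditional rule, and is not stated. But separate lesion regions do not remove their counts from the marrow contour, and the reference to recommendations is general and does not mention involved vertebrae. If exclusion is intended, the substitute region still has to be named, because the result depends on it.

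It is also fair that the size rests on assumed inputs. With entry limited to three lesions, or five on PET, L3-L5 disease may be uncommon. The top of the range needs a whole vertebra replaced at ten times normal uptake.

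A reader might go further and infer that the error pushes the substudy toward its hypothesis that more than 30% of men would have needed a plan change. The documents do not support that. The relevant criterion, "Normal organ doses within tolerance limits", names no organ and no limit. The dose limits in section 6.4 cover cord, lung, heart, esophagus, brachial plexus, liver, kidneys and small bowel, and omit marrow. More than 30% of 20 is at least 7 men, so two to four affected men could not reach it alone. They would count only if marrow had a limit that the error crossed and those men did not already fail the tumour-dose criterion.

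**Conclusion.** The rule as written gives a wrong marrow value in any man with a lesion in L3-L5 whose uptake differs from normal. The factor is 1 + f(r − 1): 1.05 to 4.0 over the assumed ranges, or 1.04 to 3.5 with the lesion counted in the true total. The direction is upward if r > 1, which section 4.4 supports, and is less certain at infusion #6. The documents give neither f, r nor the number of men with L3-L5 disease, so the effect on group results cannot be stated.

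The consequences stay within the exploratory companion study: reported marrow dose, its variability between patients, and its apparent relation to tumour burden. An effect on the >30% hypothesis is possible only if marrow is one of the organs checked. PFS, the sample size, the toxicity stopping rule and patient care are untouched.

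**What to change.** In the image quantification row of Appendix IX, state that marrow concentration comes only from vertebrae with no known metastasis on baseline imaging and outside any SABR field. Use the members of L3-L5 that qualify, or otherwise the nearest qualifying vertebrae in the field of view. As an alternative, subtract the lesion region from both the activity and the mass of the L3-L5 contour. Record which vertebrae were used for each man at each infusion, and flag men in whom none qualifies. State also that the reported quantity is the dose to uninvolved marrow, with lesions reported separately.

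The change takes a few sentences and no new imaging. Entry scans locate the lesions, the first SPECT/CT includes a diagnostic-quality CT, and the chest and abdomen views offer other vertebrae. The cost is a smaller region and noisier marrow counts in some men.

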 - o TRIAD
- Storing images (and for how long), and interpreting these images
 - o Images and data related to dosimetry will be transferred back to TRIAD

APPENDIX XI: BAYER PATIENT RELEASE CARD

Please print and fill out the card for all patient's randomized to the SABR + Xofigo Arm.

Xofigo® radium Ra 223 dichloride injection	
Hospital: _____	
Address: _____	
Patient: _____	
This patient has been administered Xofigo®	
Activity administered: _____	
Procedure date: _____	Time: _____
24-hour contact name and number: _____	
Discard this card after _____ (days/date) post-administration
